1.3 PROTOCOL SYNOPSIS

TITLE: Combination Therapy with the Proteasome Inhibitor

Carfilzomib for the Antibody-Mediated Rejection Diagnosis in

Lung Transplantation Trial (PICARD-Lung)

Protocol number: PRO15010152

Study drug: Carfilzomib (Kyprolis®)

Phase: phase II

Patient enrollment: 30

Indication: Antibody mediated rejection after lung transplantation

Sponsor: [name]

DATE: 09/20/2018

Objectives

1: To test the hypothesis in a prospective interventional clinical trial that addition of carfilzomib to conventional therapy will result in depletion of the immunodominant DSA.

- 2: To test the hypothesis in a prospective interventional clinical trial that addition of carfilzomib to conventional therapy will result in improved or stabilized allograft function.
- 3: To test the hypothesis that lung transplant recipients with AMR have effector B cell/plasma cell populations that can be identified and characterized, and that carfilzomib alters these immune mechanisms.

Study design

Phase II, prospective, open-label, single-arm active treatment, single center pilot clinical trial of the addition of carfilzomib to conventional therapy for AMR after lung transplantation.

Outcome measures

Primary endpoint: absolute change in DSA strength, titer, and complement fixation from day 1 to day 42.

Secondary endpoints:

Absolute change in DSA strength, titer, and complement fixation from day 1 to day 90 and from day 42 to day 90

Absolute change in forced expiratory volume in 1 second (FEV1) from day 1 to day 42 and to day 90.

Presence or absence of pathologic changes consistent with AMR on transbronchial biopsy from day 1 to day 42.

Patient death at any time after day 1 attributable to AMR.

Safety endpoints:

Non-lung irreversible end-organ failure (e.g., end-stage renal disease) any time after day 1 attributable to carfilzomib.

Incidence of adverse effects (AE) requiring dose-modification any time during days 1-16.

Incidence of any AE at any time after day 1 as graded by the NIH Common Terminology Criteria for Adverse Events (CTCAE) (appendix B) criteria.

Incidence of hypogammaglobulinemia any time after day 1.

Incidence of culture-proven *de novo* infection any time after day 1.

Diagnosis of systemic inflammatory response syndrome (SIRS) any time during days 1-16

Patient death at any time after day 1 to day 90 attributable to carfilzomib.

Retrospective control group:

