4.4.2 Secondary endpoints

Secondary endpoints of this study include the following:

- 4.4.2.1 Absolute change in DSA strength, titer, and complement fixation from day 1 to day 90 and from day 42 to day 90. DSA strength will be determined by Luminex single-antigen bead testing in the neat serum and quantitated in units of mean fluorescent intensity. DSA titer will be determined by Luminex single-antigen bead testing in the diluted serum to 1:16 and quantitated in units of mean fluorescent intensity. DSA complement fixation will be determined by C1q-based Luminex single-antigen bead testing in the neat serum and quantitated in units of mean fluorescent intensity.
- 4.4.2.2 Absolute change in forced expiratory volume in 1 second (FEV1) from day 1 to day 42 and to day 90. FEV1 will be quantitated via UPMC PFT lab standard methods on routine pulmonary function testing obtained in the routine clinical care of these patients.
- 4.4.2.3 Presence or absence of pathologic changes consistent with AMR on transbronchial biopsy from day 1 to day 42. Pathologic changes consistent with AMR will be defined as follows: Complement-4d fixation on >50% (diffuse) of the capillaries in the biopsy by standard immunoperoxidase method, capillaritis by standard hematoxylin and eosin (H&E) stain; or endothelialitis by standard H&E stain.
- 4.4.2.4 Patient death at any time after day 1 attributable to AMR.
- A 1:1 retrospective control group including lung transplant recipients from the University of Pittsburgh with Antibody Mediated Rejection will be created to describe differences in the endpoints using the CFZ-based regimen vs. historic standard of care.

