4.4.3 Safety outcomes

Safety outcomes of the study include the following:

- 4.4.3.1 Non-lung irreversible end-organ failure (e.g., end-stage renal disease) any time after day 1 attributable to carfilzomib.
- 4.4.3.2 Incidence of adverse effects (AE) requiring dose-modification (see section 5.3.1.2) any time during days 1-16.
- 4.4.3.3 Incidence of any AE at any time after day 1 as graded by the NIH Common Terminology Criteria for Adverse Events (CTCAE) (appendix B) criteria, as follows:
 - Grade 1: Mild; asymptomatic or mild symptoms; clinical or diagnostic observations only; intervention not indicated.
 - Grade 2: Moderate; minimal, local or noninvasive intervention indicated; limiting ageappropriate instrumental ADL (Instrumental ADL refer to preparing meals, shopping for groceries or clothes, using the telephone, managing money, etc.).
 - Grade 3: Severe or medically significant but not immediately life-threatening; hospitalization or prolongation of hospitalization indicated; disabling; limiting self-care ADL (self-care ADL refer to bathing, dressing and undressing, feeding self, using the toilet, taking medications, and not bedridden).
 - Grade 4: Life-threatening consequences; urgent intervention indicated.

Grade 5: Death related to AE.

- 4.4.3.4 Incidence of hypogammaglobulinemia any time after day 1.
- 4.4.3.5 Incidence of culture-proven *de novo* infection any time after day 1.
- 4.4.3.6 Diagnosis of systemic inflammatory response syndrome (SIRS) any time during days 1-16; requiring at least 2 of the following 4 criteria:

Body temperature: < 36 or > 38 degrees Celsius

Tachycardia: > 90 beats per minute

Tachypnea: > 20 breaths per minute

White blood cells: < 4000 or > 12000 cells/mm³

- 4.4.3.7 Patient death at any time after day 1 attributable to carfilzomib.
- A 1:1 retrospective control group including lung transplant recipients from the University of Pittsburgh with Antibody Mediated Rejection will be created to describe differences in the endpoints using the CFZ-based regimen vs. historic standard of care.

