5.13 Statistical methods

Data will only be analyzed in aggregate at study conclusion for the final enrolled patient on the efficacy and safety outcomes.

Descriptive statistics will be used to describe baseline and study characteristics of patients. Univariate parametric and nonparametric assessments, where appropriate, will be used to assess change from baseline in the efficacy and safety outcomes. Kaplan-Meier method will be used to describe freedom from endpoints and mortality in the patients treated with carfilzomib. Kaplan-Meier method will be used to visually represent the time to events and overall event rate in the patients in this pilot, not to compare events to any other group.

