5.13.3 Determination of sample size

The sample size for this trial is based on perceived appropriate enrollment of 10 patients per year for 3 consecutive years. Since this is a single-arm, active-treatment study, no such calculation of statistical power is needed to quantitate the sample size.

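### Kaplan-Meier is the only planned method for event rates, and the plan does not say how deaths from other causes enter the curves for cause-specific and non-fatal endpoints

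*Combined protocol and SAP*

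**What the plan says.** Section 5.13 Statistical methods, repeated in the synopsis, names one time-to-event method: "Kaplan-Meier method will be used to describe freedom from endpoints and mortality in the patients treated with carfilzomib". It adds that "Kaplan-Meier method will be used to visually represent the time to events and overall event rate in the patients in this pilot", and that no comparison with another group is intended. It does not list which endpoints get a curve. The public text contains no censoring rule, no cumulative incidence function and no mention of competing events.

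The endpoints that the word could cover include:

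- a secondary endpoint in section 4.4.2: "Patient death at any time after day 1 attributable to AMR";
- a safety outcome in section 4.4.3: "Patient death at any time after day 1 attributable to carfilzomib" (the synopsis ends this one at day 90; section 4.4.3 gives no end);
- a further safety outcome in section 4.4.3: "Non-lung irreversible end-organ failure (e.g., end-stage renal disease) any time after day 1 attributable to carfilzomib";
- hypogammaglobulinemia and new culture-confirmed infection, also in section 4.4.3, counted from day 1 with no stated end.

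On follow-up, section 5.4 sets study follow-up to day 90 and then a review of available records up to day 360. Section 6.3.4 records deaths from all causes as SAEs. For the time after day 90 it mentions only deaths from AMR progression as kept for analysis, and section 6.2.1 restricts later SAE recording to drug-related events.

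**The concern.** Death from another cause does not hide a later AMR death or infection; it makes it impossible. Censoring that patient treats the event as still possible and spreads the patient's weight over those who remain at risk. One minus Kaplan-Meier then estimates the risk in a hypothetical population in which nobody dies of anything else. That is not the overall event rate the section promises.

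Competing deaths are plausible here. Under section 4.3.6 a patient can qualify for the AMR diagnosis through new hypoxemia or a need for mechanical ventilation, and record review runs for most of a year. At stake is the accuracy of the descriptive rates. These matter because a single-arm pilot produces estimates rather than tests, and section 4.1 presents the trial as a source of planning information for larger controlled studies, although it speaks there of the response rate.

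**Working it through.** **The plan's own figure.** The only design number is the sample size: "Patient enrollment: 30", based on "perceived appropriate enrollment of 10 patients per year for 3 consecutive years". 10 × 3 = 30, which agrees. The plan states no event rate, alpha or power ("no such calculation of statistical power is needed to quantitate the sample size"), so there is no event rate to reproduce.

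**Inputs.** The true cumulative incidence of the event, p1, and of competing death, p2, are both assumptions. The documents give neither, so a range is shown.

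**Constant-hazard calculation.** With constant cause-specific hazards:

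- total cumulative hazard H = −ln(1 − p1 − p2);
- the event's share is H × p1/(p1 + p2);
- with other deaths censored, 1 − KM = 1 − exp[−H × p1/(p1 + p2)].

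For p1 = p2 = 20%: H = −ln(0.6) = 0.511; the event's share is 0.255; 1 − exp(−0.255) = 22.5%.

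| True event p1 | Competing death p2 | Shown by 1 − KM | Excess (points) |
|---|---|---|---|
| 20% | 0% | 20.0% | 0 |
| 10% | 10% | 10.6% | 0.6 |
| 20% | 10% | 21.2% | 1.2 |
| 20% | 20% | 22.5% | 2.5 |
| 30% | 30% | 36.8% | 6.8 |
| 20% | 40% | 26.3% | 6.3 |

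For event incidences of 10% to 50%, the relative excess is about 3% when competing deaths are 5%, 6–7% at 10%, 12–15% at 20%, and 29–44% at 40%.

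**Exact example with 30 patients.** Take 6 events, 6 competing deaths and no other censoring. The cumulative incidence is 6/30 = 20.0% whatever the order.

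- All events before the competing deaths: 1 − KM = 1 − 24/30 = 20.0%. No excess.
- Events and deaths in random order: 22.5% on average.
- All competing deaths before the events: 24 remain at risk and 18 stay event-free, so 1 − KM = 1 − 18/24 = 25.0%.

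The excess therefore depends on order as well as number. It arises only when a competing death comes before a later event.

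**Scale.** One patient in 30 is 3.3 points. The 95% Wilson interval for 6/30 is about 9.5% to 37.3%.

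**The case against.** The strongest reply is that censoring is inferred. Section 5.13 is silent, and two readings that fit the silence carry no such bias. One is a composite of the endpoint or any death, which the pairing of endpoints with mortality could mean. The other keeps patients who died as event-free to a fixed horizon, which with complete follow-up returns the simple proportion. This stands: the documents do not show that other deaths will be censored. It does not remove the point. A composite would turn both attributable-death endpoints into all-cause mortality and erase the distinction drawn in sections 4.4.2 and 4.4.3, and the fixed-horizon rule is nowhere stated. A rule is needed either way.

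The second reply is size and use. The curves are descriptive, and no test, sample size or stopping rule depends on them. Section 5.13.2 lists AEs by patient and SAEs separately, so individual deaths to day 90 will be visible. In moderate scenarios the excess is less than one patient in 30 and small beside the sampling error. This also stands, and it limits how much weight the point deserves. But a wide interval does not excuse an avoidable error that always runs in one direction.

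Two stronger conclusions are tempting. A reader might infer that every cause-specific or non-fatal curve will be biased upward. That does not follow: the excess is zero unless a competing death comes first, and SIRS and dose-modifying AEs are confined to days 1–16 of an inpatient stay, which leaves little room for it. A reader might also infer that the AMR, carfilzomib and other-death curves would add to more than all-cause mortality. Censored curves can do this (at 30% and 30%, two curves sum to 2 × 36.8% = about 74% against a true 60%), but the documents plan neither an other-death curve nor any summing.

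**Conclusion.** The point holds in a limited form. Kaplan-Meier is the only method planned for showing event rates, several endpoints are precluded by death from other causes, and the plan does not say how those deaths are handled. Under conventional censoring, one minus Kaplan-Meier is never below the cumulative incidence and can exceed it. Kaplan-Meier for all-cause mortality is sound.

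The size rests on assumed rates and constant hazards. It is zero with no competing deaths, 0.6 points at 10% and 10%, 2.5 points at 20% and 20%, and 6.8 points at 30% and 30%. The last case needs 60% of patients to have either the event or a competing death, which the documents neither support nor exclude. Larger values are more plausible for follow-up to day 360 than to day 90. The change is worth making because the better estimator costs almost nothing, but no inference in the trial depends on it.

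**What to change.** In section 5.13 and the synopsis:

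1. Name the endpoints that will have a time-to-event curve.
2. For cause-specific deaths and non-fatal events, use the cumulative incidence (Aalen-Johansen) estimator with death from other causes as a competing event. For AMR-attributable death, the competing event is death from any other cause; for a non-fatal event, it is any death.
3. Keep Kaplan-Meier for all-cause mortality, or for a composite that includes any death.
4. State the horizon. Either take the date and cause of every death from the record review to day 360, or limit these curves to day 90, where all deaths are already recorded as SAEs. Sections 6.2.1 and 6.3.4 do not clearly secure deaths from other causes after day 90, so a change to section 5.13 alone would not be enough for the longer horizon.

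The cost is a few sentences and slightly more analysis work in standard software. The downside of the longer horizon is its reliance on records that section 5.4 describes as available only in part; patients whose records stop would be censored at last contact.

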5.13.1 Analysis of the conduct of the study

Enrollment, protocol violations, and discontinuations from the study will be summarized by patient.

Demographic and baseline characteristics will be summarized using means, standard deviations, medians, interquartile ranges. All summaries will be presented by group.

Study drug administration data will be listed by dose level, and any dose modifications will be flagged. Means and standard deviations will be used to summarize the total dose of carfilzomib received. All summaries will be presented by group.

5.13.2 Safety analyses

All AE data will be listed by patient, cycle, and dose. All AE occurring after informed consent is given will be summarized by event, system, and grade. All SAE will be listed and summarized separately.

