6.1.2 Adverse effect (AE) definition

An AE is any unfavorable and unintended sign, symptom, or disease temporarily associated with the use of an investigational medicinal product or other protocol-imposed intervention, regardless of attribution.

This includes the following:

AEs not previously observed in the patient that emerge during carfilzomib therapy (days 1through 16, and 28, 42, 90), including signs or symptoms associated with AMR that were not present prior to the AE reporting period.

Complications that occur as a result of protocol-mandated interventions.

AEs that occur prior to the assignment of study treatment that are related to a protocol-mandated intervention.

Preexisting conditions judged by the investigators to have worsened in severity or frequency or changed in character during carfilzomib therapy (days 1through 16, and 28, 42, 90).

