6.2.1 Adverse event reporting period

After informed consent is obtained but before any administration of study drug, only SAEs due to protocol mandated interventions will be recorded. Any AE or SAE at any time after the first infusion of carfilzomib is initiated until day 16, and on days 28, 42, 90 ±14 days must be recorded by the investigators and reported to Amgen as defined in this section. After this period, only SAEs deemed to be related to study drug will be recorded and reported.

Serious Adverse Event Reporting Contact Information:

Amgen Global Safety

Toll-free #:[name]

For countries where the U.S. toll-free # cannot be used: [contact]

Email (Only for sponsors with a secure email connection with Amgen):

[contact]

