6.3.5 Preexisting medical conditions

A preexisting medical condition is one that is present at the time of informed consent. Such conditions shall be recorded in the study database.

A preexisting condition will only be recorded as an AE or SAE if the frequency, severity, or character of the condition worsens during the study. When recording such events, the investigators will make note of the characteristics that have worsened (e.g., increased systolic blood pressure for preexisting hypertension).

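### Adverse event summary, recording, definition and preexisting-condition rules start at different points, so the planned table cannot be built and pre-infusion events have no settled place

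*Combined protocol and SAP*

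**What the plan says.** Five sections set a start point for AEs.

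- **Summary (5.13.2).** "All AE occurring after informed consent is given will be summarized by event, system, and grade". The same section adds: "All AE data will be listed by patient, cycle, and dose". SAEs are also listed and summarised on their own.
- **Recording (6.2.1).** "After informed consent is obtained but before any administration of study drug, only SAEs due to protocol mandated interventions will be recorded". Full recording then covers "Any AE or SAE at any time after the first infusion of carfilzomib is initiated until day 16", followed by the later visits.
- **Definition (6.1.2).** One limb covers "AEs not previously observed in the patient that emerge during carfilzomib therapy". Another covers "AEs that occur prior to the assignment of study treatment that are related to a protocol-mandated intervention", with no restriction to serious events.
- **Preexisting conditions (6.3.5).** "A preexisting medical condition is one that is present at the time of informed consent". Such a condition becomes an AE only "if the frequency, severity, or character of the condition worsens during the study".
- **Safety outcome (4.4.3.3, and the synopsis).** AE incidence is counted at any time after day 1.

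No section defines a treatment-emergent AE or provides a separate table for events before the first infusion.

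**The concern.** An AE table for an added drug should separate what was present before exposure from what began or worsened after it. That requires the definition, the recording rule, the baseline and the summary to share one reference time. Here they do not.

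The interval between consent and first infusion is not clinically empty. Patients may qualify through new hypoxia or ventilation (4.3.6), catheters go in before any therapy, and on day 1 plasma exchange precedes carfilzomib (5.3 and Appendix A).

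AE incidence is a named safety outcome, and 3.1 says that the trial will establish the safety of the combination. If an event's status before the first infusion is not captured at the time, it may be hard to reconstruct at analysis.

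**Working it through.** The plan gives no figure to reproduce, so the check sets the rules side by side and follows each kind of event through them.

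**Step 1: is there an interval?** Consent must precede study-specific screening tests (5.5). Appendix A puts screening and enrolment on day 0 and the first infusion on day 1. The pregnancy test, a research procedure, may be done up to 7 days before study drug (5.4.1). The interval's length is not stated; I assume 1 to 7 days. Because carfilzomib is given between plasma exchange and immunoglobulin on exchange days, and day 1 is one, the first exchange falls inside the interval.

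**Step 2: follow an event that starts in the interval.**

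| Event | Recorded before infusion (6.2.1)? | Consequence |
|---|---|---|
| (i) Serious, due to a protocol-mandated intervention | Yes | Enters the 5.13.2 summary alongside post-infusion events |
| (ii) Non-serious, related to such an intervention | No | An AE under 6.1.2 and within the 5.13.2 summary, but not collected |
| (iii) Any other event, resolved before infusion | No | Not collected, although 5.13.2 speaks of all AEs after consent |
| (iv) Any other event, still present at infusion | No | Not preexisting under 6.3.5; later status contradictory |

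On (ii) and (iii): one could argue that an event unrelated to any study procedure is not yet an AE under 6.1.2, which would remove (iii). Row (ii) is enough by itself. The definition counts the event, the summary calls for it, and the recording rule leaves it out.

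On (i): the listing is by cycle and dose, and a pre-infusion event has neither.

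On (iv): 6.2.1 records any AE once the infusion has begun, which could bring the condition in. The emergent limb of 6.1.2 requires that it was not seen in the patient before, which points to leaving it out. Section 6.3.5 does not settle the matter, because its cut-off is consent.

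**Step 3: the safety outcome.** Read literally, counting after day 1 excludes all of day 1, including the hours after the first infusion. Read loosely, as from day 1 onward, it includes the hours before that infusion and the first plasma exchange. Neither reading matches consent or first infusion.

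**Step 4: is there a baseline?** Appendix A schedules a history and examination, blood count and metabolic panel on day 1. Section 5.6 places assessments on drug days before the infusion, and 5.4.1 records later changes from baseline abnormalities. Clinical and laboratory baseline data therefore exist. What is missing is a required graded AE or medical-history entry for a condition that began after consent.

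**Step 5: scale.** One patient in 30 is 1/30 = 3.3 percentage points; two are 2/30 = 6.7. This is only the weight of a patient. The documents give no count of pre-infusion events.

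**The case against.** The strongest reply is that the practical consequences are slight.

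- **Few events may qualify for pooling.** Catheter placement is described as routine care and plasma exchange is listed under standard of care in Appendix A. If neither is protocol-mandated, hardly any pre-infusion SAE would be recorded. This stands as a limit on size. It does not remove the conflict, because 5.3 places plasma exchange under study treatment and no section says which interventions count as mandated.
- **Pre-infusion SAEs can be identified.** All SAEs are also summarised separately, and 6.2.3 asks for a causality assessment to carfilzomib. This stands, but the main summary by event, system and grade would still contain them.
- **The safety outcome has its own window.** Counting after day 1 keeps events before day 1 out of that outcome. This also stands, but it adds a further start point and leaves day 1 unclear.
- **A baseline exists.** A reader might infer that events in the interval have no baseline and must appear as new on-treatment AEs. The documents do not support that. Day 1 assessments precede the infusion, the emergent limb of 6.1.2 excludes events already observed, 6.3.3 does not re-record a repeated laboratory abnormality unless it worsens, and 5.4.1 records examination findings as AEs only if judged related to study therapy. Entry as new is one possible reading of contradictory rules.

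A first-infusion anchor also has a difficulty of its own: the retrospective controls, who are to be described on the safety outcomes (4.4.3), have no infusion.

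**Conclusion.** The concern holds as an inconsistency between stated rules. Three results follow from the text: the 5.13.2 summary cannot be produced from what 6.2.1 collects; any SAE recorded before dosing is tabulated with post-dose events; and a condition arising between consent and first infusion has no required graded record and contradictory later status.

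The size is unknown and probably small. It depends on the interval (assumed 1 to 7 days), on whether plasma exchange and catheter placement count as protocol-mandated, and on event rates that the documents do not give. A reader might go further and infer that the whole AE table is materially contaminated by events before exposure; nothing in the documents shows that. The change is still worth making, because it costs little and keeps pre-exposure events out of the safety result.

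**What to change.** Use the start of the first carfilzomib infusion as the single anchor.

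- **5.13.2:** summarise AEs with onset, or worsening from the pre-infusion grade, after the first infusion begins. List recorded pre-infusion events separately.
- **6.3.5:** define a preexisting condition as one present before the first infusion, with its grade taken from the day 1 pre-infusion assessment.
- **6.1.2 and 6.2.1:** agree on which pre-infusion events are kept (serious only, or all that are protocol-related), and say whether plasma exchange and catheter placement count as protocol-mandated.
- **4.4.3.3 and the synopsis:** replace the day 1 wording with the same anchor.
- **Retrospective controls:** state the start date that corresponds to the anchor, since they have no infusion.

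The cost is wording in these sections, one field on the AE form for onset before or after the first infusion, and a short day 1 update of the medical-history entry. No treatment rule changes.
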